- During the run-in period (Cycle 1), the dose of cobimetinib can be reduced by 20 mg QD (one dose level) from 60 mg daily to 40 mg daily during Days 1-21.
- If a vemurafenib dose reduction is required during Days 1-21, the dose of vemurafenib can be reduced from 960 mg BID to 720 mg BID. No further dose reductions of vemurafenib are allowed during Cycle 1.
- Drug-related toxicities presenting during the run-in period (Cycle 1) that require a vemurafenib dose reduction should be improving or have resolved (see [Appendix 13](#)) prior to Cycle 2, Day 1.

Patients must be receiving both study treatments in order to enter the triplet treatment period (Cycle 2, Day 1).

Triplet treatment period (Cycles \geq 2)

The dose of cobimetinib can be reduced by 20 mg QD (one dose level) decrements up to two times for management of drug-related toxicities (i.e. from 60 to 40 mg and then from 40 to 20 mg), except during the run-in period when only one dose reduction is allowed. If further dose reduction is indicated after two dose reductions, the patient must discontinue cobimetinib but may continue treatment with atezolizumab and/or vemurafenib at the investigator's discretion. The dose of cobimetinib may be escalated by a maximum of one dose level (20 mg) from 20 mg QD to 40 mg QD at the investigator's discretion in patients who have previously undergone dose reduction, provided there are no safety concerns and the adverse event that resulted in the dose reduction has resolved to \leq Grade 1. Dose escalation from 40 mg QD to 60 mg QD is not permitted.

There will be no dose modifications for atezolizumab in this study.

The dose of vemurafenib dose can be reduced during the triplet combination treatment period from 720 mg BID to 480 mg BID. If further dose reduction is indicated, the patient must discontinue vemurafenib but may continue treatment with atezolizumab and/or cobimetinib at the investigator's discretion.

Dose modification guidelines for specific adverse events with combination treatment in this cohort are provided in [Appendix 13](#) . Additional guidelines for the management of adverse events associated with atezolizumab are provided in [Appendix 14](#).

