General guidance for dose modifications and treatment delays and discontinuation	
 • There will be no dose modifications for atezolizumab. • The dose of cobimetinib and vemurafenib can be reduced by one dose level in the run-in period (Cycle 1) (see Section 5.1.6.2). • During the triplet combination period (Cycles ≥ 2), the dose of cobimetinib can be reduced by 20 mg (one dose level) up to two times (i.e., from 60 mg to 40 mg and then from 40 mg to 20 mg). If further dose reduction is indicated after two dose reductions, the patient must discontinue cobimetinib but may continue treatment with atezolizumab and/or vemurafenib at the investigator's discretion. • During the triplet combination period (Cycles ≥ 2), vemurafenib dose can be reduced from 720 mg BID to 480 mg BID. If further dose reduction is indicated, the patient must discontinue vemurafenib but may continue treatment with atezolizumab and/or cobimetinib at the investigator's discretion. • If atezolizumab is withheld and corticosteroids are initiated for treatment of a toxicity, corticosteroids must be tapered over ≥ 1 month to ≤ 10 mg/day oral prednisone or equivalent before atezolizumab can be resumed. If atezolizumab is withheld for > 12 weeks, the patient should be discontinued from atezolizumab. Study treatment may be withheld for > 12 weeks to allow for patients to taper off corticosteroids prior to resuming treatment. Atezolizumab can be resumed after being withheld for > 12 weeks if the patient is likely to derive clinical benefit. The decision to re-challenge patients with atezolizumab should be based on investigator's assessment of benefit-risk and documented by the investigator (or an appropriate delegate). The Medical Monitor is available to advise as needed. Atezolizumab treatment may be suspended for reasons other than toxicity (e.g., surgical procedures). The acceptable length of treatment interruption must be based on an assessment of benefit-risk by the investigator and in alignment with the protocol requirements for the duration of treatment and documented by the investigator. The Medical Monitor is available to advise as needed. • If either cobimetinib or vemurafenib is withheld for > 28 days because of toxicity, the patient should be discontinued from that drug, unless the patient is likely to derive clinical benefit. The decision to re-challenge patients with study treatment should be based on investigator's assessment of benefit-risk and documented by the investigator (or an appropriate delegate). The Medical Monitor is available to advise as needed.

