
Appendix 13: Guidelines for Management of Patients Who Experience Specific Adverse Events in Cohort 2

General guidance and infusion-related reactions	
Event	Action to be taken
	
 After dose reduction, consideration may be given to allow for dose escalation of cobimetinib or vemurafenib by a maximum of one dose level following resolution of the adverse event that resulted in dose modification, provided there are no safety concerns. Dose escalation is not permitted during the run-in period (Cycle 1). See Section 5.1.6.2.
IRRs, anaphylaxis and hypersensitivity reaction	
 Guidelines for management of IRRs are provided in the Atezolizumab Investigator's Brochure for atezolizumab. For anaphylaxis precautions, see Appendix 11 . For severe hypersensitivity reactions, permanently discontinue all study treatment.

IRR = infusion-related reaction.

Table 2: Gastrointestinal Toxicity

Gastrointestinal toxicity	
Event	Action to be taken
Gastrointestinal events: general guidance	
 All events of diarrhoea or colitis should be thoroughly evaluated for other more common aetiologies. For events of significant duration or magnitude or associated with signs of systemic inflammation or acute phase reactants (e.g., increased CRP, platelet count, or bandemia): 
 Perform sigmoidoscopy (or colonoscopy, if appropriate) with colonic biopsy, with three to five specimens for standard paraffin block to check for inflammation and lymphocytic infiltrates to confirm colitis diagnosis.

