Photosensitivity, Grade 1	
 Continue all study treatment. Initiate supportive care.
Photosensitivity, Grade 2	
 Continue atezolizumab. Initiate supportive care per institutional guidelines. 
First episode:
 
 If event does not resolve to Grade 1 or better within 7 days, withhold cobimetinib and vemurafenib. If treatment is withheld and event resolves to Grade 1 or better within 28 days, resume cobimetinib at current dose and resume vemurafenib with dose reduced by one level. If event does not resolve to Grade 1 or better within 28 days, permanently discontinue cobimetinib and vemurafenib. 
Subsequent episodes:
 
 Withhold cobimetinib and vemurafenib. If event resolves to Grade 1 or better within 28 days, resume cobimetinib at current dose and resume vemurafenib with dose reduced by one level. If event does not resolve to Grade 1 or better within 28 days, permanently discontinue cobimetinib and vemurafenib.
Photosensitivity, Grade 3	
 Withhold cobimetinib and vemurafenib. Continue atezolizumab Initiate supportive care per institutional guidelines. If event resolves to Grade 1 or better within 28 days, resume cobimetinib at current dose and resume vemurafenib with dose reduced by one level. If not, permanently discontinue cobimetinib and vemurafenib.
Photosensitivity, Grade 4	
 Initiate supportive care per institutional guidelines. If event resolves to Grade 1 or better within 28 days, resume cobimetinib at current dose and resume vemurafenib with dose reduced by one level. If not, permanently discontinue cobimetinib and vemurafenib. Continue atezolizumab if clinically indicated.

Appendix 13: Guidelines for Management of Patients Who Experience Specific Adverse Events in Cohort 2

Dermatologic toxicity	
Event	Action to be taken
Dermatologic event, Grade 1	
 Continue all study treatment. Initiate maximum supportive care (e.g., antihistamines, topical corticosteroids).

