ALT or AST > 3 × ULN to 5 × ULN in combination with bilirubin ≤ 3 × ULN (triple combination period/Cycles ≥ 2)	
 Consider withholding all study treatment. Monitor ALT, AST and bilirubin at least weekly. If values worsen, monitor at least every other day. If values have not worsened and have not resolved to ≤ 3 × ULN upon re-evaluation 1–20 days after event onset, consider treatment with 1–2 mg/kg/day oral prednisone or equivalent. If values have not worsened and have not resolved to ≤ 3 × ULN upon re-evaluation ≥ 21 days after event onset, initiate treatment with 1–2 mg/kg/day oral prednisone or equivalent. If values have worsened upon re-evaluation, initiate treatment with 1–2 mg/kg/day IV methylprednisolone or equivalent and convert to 1–2 mg/kg/day oral prednisone or equivalent upon improvement. If values do not improve within 48 hours after initiating corticosteroids, consider adding an immunosuppressive agent. If treatment is withheld and values resolve to ≤ 3 × ULN before or within 12 weeks after initiation of corticosteroids, resume atezolizumab at fixed dose [a, b]. If values do not resolve to ≤ 3 × ULN within 12 weeks after initiation of corticosteroids, permanently discontinue atezolizumab [a, b, c]. If treatment is withheld and values resolve to ≤ 3 × ULN before or within 28 days after initiation of corticosteroids, resume cobimetinib and vemurafenib as follows: 
 If values did not worsen prior to resolution, resume cobimetinib and vemurafenib at current doses. If values worsened prior to resolution: 
 First Episode: Resume cobimetinib at current dose and resume vemurafenib with dose reduced by one level. Second Episode: Resume cobimetinib and vemurafenib with doses reduced by one level. Third Episode: Resume cobimetinib with dose reduced by one level and permanently discontinue vemurafenib. Fourth Episode: Permanently discontinue cobimetinib. If values do not resolve to ≤ 3 × ULN within 28 days after initiation of corticosteroids, permanently discontinue cobimetinib and vemurafenib.

Appendix 13: Guidelines for Management of Patients Who Experience Specific Adverse Events in Cohort 2

Elevated liver enzymes	
Event	Action to be taken

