ALT or AST > 5 × ULN to 10 × ULN in combination with bilirubin ≤ 1.5 × ULN (triple combination period/Cycles ≥ 2)	
 Withhold all study treatment. Monitor ALT, AST and bilirubin at least every other day. If values do not improve within 48 hours, initiate treatment with 1–2 mg/kg/day IV methylprednisolone or equivalent and convert to 1–2 mg/kg/day oral prednisone or equivalent upon improvement. If values do not improve within 48 hours after initiating corticosteroids, consider adding an immunosuppressive agent. If values improve within 48 hours but subsequently worsen or do not resolve to ≤ 3 × ULN within 14 days after event onset, initiate treatment with 1–2 mg/kg/day IV methylprednisolone or equivalent and convert to 1–2 mg/kg/day oral prednisone or equivalent upon improvement. If values do not improve within 48 hours after initiating corticosteroids, consider adding an immunosuppressive agent. If values resolve to ≤ 3 × ULN before or within 12 weeks after initiation of corticosteroids, resume atezolizumab at fixed dose [a, b]. If values do not resolve to ≤ 3 × ULN within 12 weeks after initiation of corticosteroids, permanently discontinue atezolizumab [a, b, c]. If values resolve to ≤ 3 × ULN before or within 28 days after initiation of corticosteroids, resume cobimetinib and vemurafenib as follows: First Episode: Resume cobimetinib at current dose and resume vemurafenib with dose reduced by one level. Second Episode: Resume cobimetinib and vemurafenib with doses reduced by one level. Third Episode: Resume cobimetinib with dose reduced by one level and permanently discontinue vemurafenib. Fourth Episode: Permanently discontinue cobimetinib. If values do not resolve to ≤ 3 × ULN within 28 days after initiation of corticosteroids, permanently discontinue cobimetinib and vemurafenib.

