- Patients on a cobimetinib dose less than 60 mg will reduce by one dose level reduction (a 20-mg daily reduction), from a 40 mg daily dose to a 20 mg daily dose, and patients on a 20 mg daily dose at the time of the interruption (for LVEF decline) should discontinue cobimetinib.

Appendix 13: Guidelines for Management of Patients Who Experience Specific Adverse Events in Cohort 2

Table 13: Rhabdomyolysis or CPK Elevation

Rhabdomyolysis or CPK elevation	
Event	Action to be taken
General guidance	
 Consider withholding cobimetinib while investigating aetiology. Continue atezolizumab and vemurafenib. Assess patient for any history of strenuous physical activity, blunt trauma, or recent intramuscular injections. Evaluate for cardiac injury and rhabdomyolysis. If evidence of clinically significant cardiac injury or rhabdomyolysis, consider permanent discontinuation of cobimetinib.
Asymptomatic CPK elevation, Grade 1, 2, or 3	
 Continue all study treatment.
Rhabdomyolysis or symptomatic CPK elevation, Grade 1, 2, or 3	
 Withhold cobimetinib. Continue atezolizumab and vemurafenib. If event improves by at least one grade within 28 days, resume cobimetinib with dose reduced by one level. If not, permanently discontinue cobimetinib.
Rhabdomyolysis or CPK elevation (symptomatic or asymptomatic), Grade 4	
 Withhold cobimetinib. Continue atezolizumab and vemurafenib. If event improves to Grade \leq 3 within 28 days, resume cobimetinib with dose reduced by one level. If not, permanently discontinue cobimetinib.
Grade 3 or 4 or intolerable Grade 2 treatment-related toxicities not described above	
 Withhold all study treatment. If event resolves to Grade 1 or better within 12 weeks, resume atezolizumab at fixed dose. If not, permanently discontinue atezolizumab [a, b, c]. If event resolves to Grade 1 or better within 28 days, resume cobimetinib and vemurafenib with doses reduced by one level. If not, permanently discontinue cobimetinib and vemurafenib.

CPK = creatine phosphokinase.

- If corticosteroids have been initiated, they must be tapered over \geq 1 month to \leq 10 mg/day oral prednisone or equivalent before atezolizumab can be resumed.

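### Cohort 2, Cycles 2 and later: two liver rows in Appendix 13 Table 5 resume vemurafenib at a second reduced dose, where Section 5.1.6.2 and Appendix 13 Table 1 require it to be stopped

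*Protocol*

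**What the plan says.** **General rule.** Protocol Section 4.3.2.2 (Table 3) schedules vemurafenib at 720 mg BID from Cycle 2. For the triplet period, Section 5.1.6.2 permits a reduction to 480 mg BID and continues: "If further dose reduction is indicated, the patient must discontinue vemurafenib but may continue treatment with atezolizumab and/or cobimetinib". Appendix 13 Table 1 says the same for Cycles 2 and later: "vemurafenib dose can be reduced from 720 mg BID to 480 mg BID. If further dose reduction is indicated, the patient must discontinue vemurafenib". Table 1 also permits optional re-escalation once the adverse event has resolved: "consideration may be given to allow for dose escalation of cobimetinib or vemurafenib by a maximum of one dose level".

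**Liver rows.** Two rows of Appendix 13 Table 5 for Cycles 2 and later give instructions by episode.

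- At episode 1, cobimetinib stays unchanged and vemurafenib goes down one level.
- At episode 2, both drugs are restarted at a lower dose: "Resume cobimetinib and vemurafenib with doses reduced by one level".
- At episode 3, vemurafenib is withdrawn while cobimetinib is lowered again: "Resume cobimetinib with dose reduced by one level and permanently discontinue vemurafenib".
- At episode 4, cobimetinib is stopped.

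In the row for ALT/AST above 5 to 10 times ULN with bilirubin at most 1.5 times ULN, treatment is always withheld and this ladder always governs resumption. In the row for ALT/AST above 3 to 5 times ULN with bilirubin at most 3 times ULN, withholding is only to be considered. There the ladder applies after withholding under the condition "If values worsened prior to resolution"; otherwise both drugs resume at their current doses.

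**Photosensitivity row.** For subsequent episodes of Grade 2 photosensitivity, Appendix 13 Table 4 says: "If event resolves to Grade 1 or better within 28 days, resume cobimetinib at current dose and resume vemurafenib with dose reduced by one level". This row is not confined to Cycles 2 and later.

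**The concern.** A patient on 480 mg BID who has a second qualifying liver episode is covered by two instructions that cannot both be followed. The Table 5 row says to resume vemurafenib one level lower. Section 5.1.6.2 and Table 1 say that when a further reduction is called for, the drug must stop. The row also gives no usable dose, because the protocol names no level below 480 mg BID.

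What is at stake is consistent handling of an expected toxicity. Section 5.1.5.2 says that Grade 3 or higher ALT or AST elevations may occur more often with the triplet. A site that follows the row literally departs from a mandatory rule in the protocol body. A site that follows the body disregards the row written for that exact event.

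**Working it through.** No statistical quantity is involved, so the check traces the dose through the text.

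**Inputs**

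- Named vemurafenib levels: 960, 720 and 480 mg BID (Sections 4.3.2.2 and 5.1.6.2).
- Size of one level: 960 − 720 = 240 mg and 720 − 480 = 240 mg, that is, one 240-mg tablet per dose.
- Starting dose in Cycles 2 and later: vemurafenib 720 mg BID, cobimetinib 60 mg QD.
- Permitted reductions in the triplet period (Section 5.1.6.2): vemurafenib one (720 to 480); cobimetinib two (60 to 40, then 40 to 20).

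**Tracing the Table 5 ladder, assuming each episode resolves in time and there is no re-escalation**

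| Episode | Cobimetinib instruction | Cobimetinib dose (QD) | Vemurafenib instruction | Vemurafenib dose (BID) |
|---|---|---|---|---|
| 1 | unchanged | 60 mg | down one level | 720 − 240 = 480 mg |
| 2 | down one level | 60 − 20 = 40 mg | down one level | 480 − 240 = 240 mg, not a named dose |
| 3 | down one level | 40 − 20 = 20 mg | stop | stopped |
| 4 | stop | stopped | already stopped | stopped |

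For cobimetinib the ladder fits: two reductions, then stop, matching the two that Section 5.1.6.2 allows. For vemurafenib it needs two reductions before the stop, and Section 5.1.6.2 allows one. Under the general rule the stop belongs at episode 2; the rows put it at episode 3.

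**When the conflict arises**

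- *Above 5 to 10 times ULN row:* a patient who resumed vemurafenib after the first episode did so at a reduced dose, so the second episode meets the conflict unless the patient was re-escalated to 720 mg BID.
- *Above 3 to 5 times ULN row:* the conflict needs the patient to be at 480 mg BID already and the second episode to have been withheld and to have worsened. If the first episode did not lead to a reduction, the second takes the patient from 720 to 480 mg BID, which is allowed.
- *Grade 2 photosensitivity row:* the first-episode reduction applies only if the event failed to resolve within 7 days and drug was withheld. A later episode may therefore bring the patient's first reduction. If the first reduction was in the run-in (960 to 720), one further step to 480 mg BID in the triplet period is allowed. The conflict arises only for a patient already at 480 mg BID.

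**The case against.** The strongest defence is that the floor is already written. Section 5.1.6.5 limits dose modifications to those permitted, and Table 1 is the general guidance for the whole appendix. A row calling for one level less at 480 mg BID could then simply mean that a further reduction is indicated, so the drug stops. That reading works for the many Appendix 13 rows that order a one-level reduction without counting episodes. It does not work for these two. They direct that vemurafenib be resumed at the second episode and reserve permanent discontinuation for the third, so they assume the patient is still taking it in between.

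Two further replies stand in part. Re-escalation under Table 1 removes the conflict for a patient returned to 720 mg BID, but it is optional and the rows do not depend on it; the triplet text of Section 5.1.6.2 describes re-escalation only for cobimetinib. Section 5.1.6.5 also says the guidelines do not replace clinical judgment. This helps a site cope, but does not settle which text governs.

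A reader might infer three stronger things that the documents do not support.

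- *That the photosensitivity row is equally contradictory.* It is not, because of its conditions on withholding and period.
- *That the run-in is contradictory for a first event on the scheduled 720 mg BID from Day 22.* Section 5.1.6.2 permits one reduction over Days 1 to 28 and names a step only for Days 1 to 21. One level below 720 can be inferred as 480 mg BID from the named levels, so this is missing detail and at most a request for clarification.
- *That a known share of patients will be affected.* Section 1.3.2.3 reports Grade 3/4 ALT increase in 5 of 39 triplet patients (12.8%). That does not count patients on this ladder: the rows use ULN multiples with bilirubin limits, and ALT above 10 times ULN means permanent discontinuation of all treatment.

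**Conclusion.** The contradiction is real and confined to the Second Episode lines of two liver rows in Appendix 13 Table 5 for Cycles 2 and later. One vemurafenib reduction is available from 720 mg BID; the ladder calls for two, and the second points to an unnamed 240 mg BID. This assumes that the patient started Cycle 2 on 720 mg BID, was reduced to 480 mg BID, and was not re-escalated. For the lower ALT/AST row it also assumes that the second episode was withheld and worsened.

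Severity is minor. The text is wrong as written and relevant to safety, but a site can resolve it in favour of the two mandatory stop rules. The documents give no frequency for second episodes, so the number of patients affected cannot be estimated. No endpoint, sample size or confidence interval changes.

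**What to change.** In the Second Episode line of both liver rows, keep the one-level cobimetinib reduction and replace the vemurafenib part with: *Resume vemurafenib at 480 mg BID only if the patient was at 720 mg BID; if already at 480 mg BID, permanently discontinue vemurafenib.* This brings the rows into line with the existing rule and still covers a re-escalated patient. The protocol already uses a floor of this kind for cobimetinib in the footnote to Appendix 13 Table 12: "patients on a 20 mg daily dose at the time of the interruption (for LVEF decline) should discontinue cobimetinib". That table prints absolute doses, so the footnote is a model for the wording and not proof of an omission elsewhere.

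As a secondary change, add the same vemurafenib sentence, limited to Cycles 2 and later, to the subsequent-episodes line of Grade 2 photosensitivity in Table 4, leaving cobimetinib at its current dose. The sponsor could also be asked to state the intended run-in dose after a first event on 720 mg BID. Naming one would be a new dosing rule and is not needed for this correction.

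The cost is a small amendment to two tables of one appendix. Under Section 9.7 it needs IRB/EC approval and, as locally required, regulatory approval before use. There is no statistical cost.

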5.1.6.3 Treatment Interruption or Discontinuation

Atezolizumab treatment may be temporarily suspended in patients experiencing toxicity considered to be related to study treatment. If corticosteroids are initiated for treatment of the toxicity, they must be tapered over \geq 1 month to \leq 10 mg/day oral prednisone or equivalent before atezolizumab can be resumed. If atezolizumab is withheld for $>$ 12 weeks, the patient will be discontinued from atezolizumab. Study treatment may be withheld for $>$ 12 weeks to allow for patients to taper off corticosteroids prior to resuming treatment. Atezolizumab can be resumed after being withheld for 12 weeks if the patient is likely to derive clinical benefit. *The decision to re-challenge patients with atezolizumab should be based on investigator's assessment of benefit-risk and documented by the investigator (or an appropriate delegate). The Medical Monitor is available to advise as needed.* Atezolizumab treatment may be suspended for reasons other than toxicity (e.g., surgical procedures). The acceptable length of treatment interruption *must be based on an assessment of benefit-risk by the investigator and in alignment with the protocol requirements for the duration of treatment and documented by the investigator.* The Medical Monitor is available to advise as needed.

Cobimetinib (Cohort 1) or cobimetinib and vemurafenib (Cohort 2) treatment may be temporarily suspended in patients who experience toxicity considered to be related to

study treatment. If cobimetinib or vemurafenib (if applicable) has been withheld for > 28 days because of toxicity, the patient should be discontinued from that drug, unless *the patient is likely to derive clinical benefit. The decision to re-challenge patients with study treatment should be based on investigator's assessment of benefit-risk and documented by the investigator (or an appropriate delegate)*. The Medical Monitor is available to advise as needed. The Medical Monitor should be consulted for any major surgery (e.g., involving a body cavity), and cobimetinib and vemurafenib (if applicable) should generally be withheld for two days prior to the procedure and for two weeks afterwards.

For dose interruptions required in the run-in period (Cycle 1) in Cohort 2, refer to Section [5.1.6.2](#).

5.1.6.4 Management Guidelines – Cohort 1

In general, toxicities should be managed with supportive care, dose modifications (as permitted), and treatment interruptions applied to the component of the study treatment judged to be the primary cause. Additional tests or procedures, such as autoimmune serology or biopsies to obtain tissue samples, may be performed to determine a possible immunogenic aetiology. This also applies to cases where the severity exceeds previously observed toxicities, or nature of the toxicity encountered differs from the known safety profile. Special attention to cases of severe cutaneous hypersensitivity reactions, such as Drug Rash with Eosinophilia and Systemic Symptoms (DRESS) is warranted from study investigators.

For management of cobimetinib- and atezolizumab-specific toxicities, including IRRs, gastrointestinal toxicity, dermatologic toxicity, hepatotoxicity, pulmonary toxicity, potential eye toxicity, reductions in LVEF from baseline, rhabdomyolysis, elevated CPK and haemorrhage, see [Appendix 12](#). Additional guidelines for the management of adverse events associated with atezolizumab are provided in [Appendix 14](#) .

5.1.6.5 Management Guidelines – Cohort 2

In general, toxicities should be managed with supportive care, dose modifications (as permitted), and treatment interruptions applied to the component of the study treatment judged to be the primary cause. Additional tests or procedures, such as autoimmune serology or biopsies to obtain tissue samples, may be performed to determine a possible immunogenic aetiology.

Cohort 2 patients should be monitored closely upon initiation of atezolizumab as a third treatment component on Days 1 and 15 of Cycles 2 and 3, as well as the days immediately following these visits. Regular telephone contact and, if needed, unscheduled laboratory tests are strongly recommended.

Guidelines for management of patients who experience specific adverse events in this cohort are provided in [Appendix 13](#). The table also includes general guidelines for dose

modifications and treatment delays and discontinuation. Additional guidelines for the management of adverse events associated with atezolizumab are provided in [Appendix 14](#). The guidelines in [Appendix 13](#) and [Appendix 14](#) are not intended to replace clinical judgment or dictate care of individual patients.

Guidelines for management of cobimetinib and vemurafenib toxicities in [Appendix 13](#) will not apply to reversible laboratory abnormalities with no clinical sequelae or no clinical significance as determined by the investigator in consultation with the Medical Monitor.

